17.1 Sample size calculation

The sample size is based on the primary objective and primary endpoint of the trial.

The primary objective of this trial is to confirm the effect of IDegLira in terms of glycaemic control in subjects with T2DM on previous treatment with SGLT2i ± OAD therapy. This will be done by

Protocol
Trial ID: NN9068-4229
UTN: U1111-1168-9343
EudraCT No.: 2015-001596-48

CONFIDENTIAL

Date: Version: Status: Page:

20 November 2015 | Novo Nordisk 2.0 Final 71 of 107

comparing the difference in change from baseline in HbA_{1c} after 26 weeks to a non-inferiority margin of 0.3% for IDegLira versus IGlar, both arms on continued SGLT2i ± OAD therapy.

The non-inferiority margin of 0.3% is due to guidance $\frac{30,31}{2}$, a treatment effect -0.85% $[-1.04; -0.66]_{95\% \text{ CI}}$ of IGlar versus placebo reported in a placebo controlled clinical trial in T2DM subjects, and the effect of IGlar stated to be clinically equal to NPH³³. With the superiority of IGlar to placebo and IGlar established as being as efficacious as NPH, a non-inferiority margin of 0.3% is considered to give sufficient assay sensitivity in this trial.

Formally, let D be the mean treatment difference (IDegLira – IGlar) in change from baseline in HbA_{1c}. The null-hypothesis of IDegLira inferior by 0.3% or more will be tested against the alternative hypothesis of non-inferiority (IDegLira inferior by less than 0.3%) as given by

$$H_0: D \ge 0.3\%$$
 against $H_A: D < 0.3\%$.

Non-inferiority will be considered confirmed if the upper bound of the two-sided 95% confidence interval for D (mean treatment difference in change from baseline in HbA_{1c}) is strictly below 0.3%. This is equivalent to using a one-sided test of size 2.5%, i.e. the Type I error rate is controlled at 2.5% one-sided.

Accordingly, the sample size is calculated using a t-statistic under the assumptions of a one-sided test of size 2.5%, a mean treatment difference of 0.0%, a standard deviation of 1.0%, a noninferiority margin of 0.3%, and that 15% of the randomised subjects will be excluded from the PP analysis set. These assumptions are based on experience from the phase 3a development programs for IDegLira and insulin degludec. With the 1:1 randomisation scheme the sample size is set to 208 subjects per treatment arm; in total 416 subjects will be randomised. This will ensure a nominal power of 80% for confirming the primary objective based on PP.

Considering inferior efficacy retention for IDegLira as opposed to IGlar amongst the anticipated 15% of subjects discontinuing randomised treatment, the expected treatment difference may be adjusted by the NI margin for discontinued subjects leading to an adjusted treatment difference of $0.85 \times 0.0\% + 0.15 \times 0.3\% = 0.045\%$. A total of 208 subjects per treatment arm will then yield a power of at least 74% (see Table 17–1)

CONFIDENTIAL

Trial ID: NN9068-4229 UTN: U1111-1168-9343 EudraCT No.: 2015-001596-48 Version: Status: Page: 2.0 Final 72 of 107

Table 17–1 Power for various rates of discontinuation

	Adjusted treatment difference (% discontinued)						
SD	0.000 (0%)	0.045 (15%)	0.060 (20%)	0.075 (25%)			
0.9	0.924	0.822	0.774	0.720			
1.0	0.863	0.737	0.685	0.629			
1.1	0.792	0.655	0.603	0.548			
1.2	0.720	0.580	0.530	0.479			

Power is computed under the assumption of 208 subjects in either arm, 1:1 randomization, and a penalty of the NI margin 0.3% in treatment difference for discontinuing subjects. SD: standard deviation.

For the confirmatory secondary endpoints body weight and hypoglycaemic episodes the marginal powers are in the order of 75% and 60% respectively under assumptions of moderate treatment effects: a treatment difference of 1 kg in weight change in favour of IDegLira, and a hypoglycaemic episode event rate of 1.8 event/PYE and rate ratio of 0.66 versus comparator. Such treatment differences have been observed for IDegLira in the phase 3a development programme. The order of hypotheses in the hierarchical testing procedure reflects this.

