6.1 Number of subjects

Number of subjects planned to be randomised and started on trial products: 416

Number of subjects expected to complete the trial (on trial product): 354

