Date: Version: Status: Page:

20 November 2015 | Novo Nordisk 2.0 Final 70 of 107

treating individual subjects with T2DM. For the confirmatory secondary endpoints de jure estimands addressing efficacy are chosen as secondary estimand too.

Only endpoints derived after 26 weeks will be analysed statistically. The expected percentage of missing data is around 15%. In accordance with guidance $\frac{29}{2}$ endpoints will be assessed at frequent visits and also on subjects who prematurely discontinue treatment. If an assessment has been made both at screening and randomisation, and if not otherwise specified, the value from the randomisation visit will be used as the baseline value. If the value measured at the randomisation visit is missing and the assessment also has been made at screening, then the screening value will be used as the baseline value.

Laboratory values below the lower limit of quantification (LLOQ) will be set to ½LLOQ.

The test strategy is hierarchical testing in order to control the familywise Type I error. Inferences will be based on the primary analyses of the primary estimands. The trial will be powered with respect to the primary objective and endpoint.

Presentation of results from a statistical analysis will include the estimated mean treatment effects using LSMean for absolute values, and change from baseline where applicable. The LSMean is either obtained by Rubin's rule weighing together LSMeans from multiple imputation estimations or obtained directly from estimation of a parameterized statistical model. In addition, estimated mean treatment difference (or ratio) will be presented together with the two-sided 95% confidence interval and corresponding two-sided *p*-value.

In the statistical models explanatory factors will be parameterized as follows:

- Treatment: IDegLira, IGlar
- Pre-trial OAD: SGLT2i ± pioglitazone(pio), SGLT2i + metformin(met) ± pio, SGLT2i + $DPP4i \pm pio$, $SGLT2i + met + DPP4i \pm pio$
- Region: Europe (Finland, Hungary, Russia, Slovakia, Slovenia, Spain, Switzerland), North America (CA, USA), South America (Argentina), Asia (India)
- Visit: Planned visits for actual endpoint according flow-chart

The impact of protocol deviations and outliers may be investigated further in sensitivity analyses if deemed relevant.

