17.3.1 Primary statistical analysis primary estimand

Multiple imputation – jump to reference – retrieved data – NI penalty

The primary objective of this trial is to confirm the effect of IDegLira in terms of glycaemic control in subjects with T2DM on previous treatment with SGLT2i ± OAD therapy.

The primary estimand for the primary objective will be the difference in change from baseline in HbA_{1c} after 26 weeks between T2DM subjects randomised to IDegLira and IGlar, both in combination with SGLT2i \pm OAD, regardless of whether subjects remained on initially assigned treatment or not until week 26. The treatment difference is to be compared to a non-inferiority margin of 0.3%.

Formally, let D be the mean treatment difference (IDegLira – IGlar) in change from baseline in HbA_{1c}. The null-hypothesis of IDegLira inferior by 0.3% or more will be tested against the alternative hypothesis of non-inferiority (IDegLira inferior by less than 0.3%) as given by

$$H_0$$
: $D \ge 0.3\%$ against H_A : $D < 0.3\%$.

Non-inferiority will be considered confirmed if the upper bound of the two-sided 95% confidence interval for D (mean treatment difference in change from baseline in HbA_{1c}) is strictly below 0.3%. This is equivalent to using a one-sided test of size 2.5%, i.e. the Type I error rate is controlled at 2.5% one-sided.

The primary estimand will be estimated based on the FAS using all post baseline HbA_{1c} measurements obtained at planned visits up to and including week 26, and data retrieved at week 26

CONFIDENTIAL

Date: Version: Status: Page:

20 November 2015 2.0 Final 74 of 107

Novo Nordisk

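### The 80% power quoted for the primary objective belongs to an unpenalised PP t-test that does not decide it; the deciding FAS analysis has about 70–74%, so 74% is not a minimum

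*Protocol*

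**What the plan says.** Section 17.1 sizes the trial with a one-sided 2.5% t-test: true difference 0.0%, SD 1.0%, margin 0.3%, and 15% of randomised subjects left out of the PP set. It sets 208 per arm and concludes: "This will ensure a nominal power of 80% for confirming the primary objective based on PP".

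The next paragraph allows for worse efficacy retention in IDegLira subjects who discontinue. It charges the margin to 15% of subjects, which gives an adjusted difference of 0.045%, and states: "A total of 208 subjects per treatment arm will then yield a power of at least 74"%. It refers to Table 17–1, whose note says: "Power is computed under the assumption of 208 subjects in either arm".

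Other sections define what decides the objective and what data are expected:

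- Section 17: "Inferences will be based on the primary analyses of the primary estimands", and "The trial will be powered with respect to the primary objective and endpoint".
- Section 17.3.1: "The primary estimand will be estimated based on the FAS". Missing values are multiply imputed, step 6 adds 0.3% to the final value of every discontinued IDegLira subject whether that value was retrieved or imputed, and step 8 pools by Rubin's rule. Protocol Amendment 2 renames the imputation approach but changes neither the penalty nor section 17.1.
- Section 17.3.2: PP appears only as a sensitivity analysis that repeats the primary analysis, penalty included.
- Section 17: "The expected percentage of missing data is around 15"%.
- Section 6.1: "Number of subjects expected to complete the trial (on trial product): 354". This implies 62 of 416 discontinuing, or 14.9%.

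**The concern.** The power figure is attached to the wrong analysis. The 80% is described as power for confirming the primary objective, yet it comes from a test with a different analysis set, no penalty and no imputation. The unpenalised PP t-test is not among the HbA1c non-inferiority analyses in section 17.3 at all.

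The second figure is closer to the deciding analysis but is worded as a minimum. It moves the mean for the penalty and keeps 208 fully informative subjects per arm. Any discontinued subject without a V32A value adds imputation variance, which the table leaves out.

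Section 17.1 is the justification for N = 416. Under section 17.4.1 all four superiority tests open only if this non-inferiority test succeeds, so its power caps the chance of every confirmatory claim.

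**Working it through.** **Inputs.** From section 17.1: one-sided alpha 0.025, margin 0.3, SD 1.0, true difference 0, 208 per arm, 15% discontinuing. From section 17.3.1: penalty 0.3, Rubin's rule. Not in the protocol, so varied: the share *r* of discontinued subjects with a V32A value, and the correlation between visits.

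**1. The protocol's PP figure.** n = 0.85 × 208 = 176.8 per arm. SE = 1.0 × √(2/176.8) = 0.1064 and the noncentrality is 0.3/0.1064 = 2.82. The noncentral t distribution gives power 0.803, so the 80% reproduces.

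**2. Table 17–1.** For SD 1.0 and 15% discontinued, the adjusted difference is 0.85 × 0 + 0.15 × 0.3 = 0.045. SE = √(2/208) = 0.0981, the noncentrality is (0.3 − 0.045)/0.0981 = 2.60, and power is 0.737. All 16 cells reproduce to within 0.001. On the same basis, 243 per arm would be needed for 80%.

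**3. Variance of the penalty.** Adding 0.3 to a random 15% of one arm adds variance 0.15 × 0.85 × 0.3² = 0.0115 in that arm. Power falls from 0.737 to 0.735.

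**4. Imputation.** Let q = 0.15 × (1 − r) be the imputed share. An approximation for imputation from the reference arm is:

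- Rubin variance: R = (2/208)(1 + q) + 0.0115/208
- sampling variance of the estimate: S = (2/208)(1 − q) + 0.0115/208
- power = Φ[(0.255 − 1.966√R)/√S]

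With r = 0, q = 0.15, √R = 0.1054 and √S = 0.0907, so power = Φ[(0.255 − 0.2073)/0.0907] = Φ(0.526) = 0.701. With r = 0.5 it is 0.718 and with r = 1 it is 0.735. The loss arises because Rubin's standard error grows with imputation while the spread of the estimate shrinks.

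**5. Simulation of steps 1–8.** Six HbA1c visits; IDegLira discontinuers without V32A set wholly to missing; IGlar values before discontinuation kept; imputation models fitted to IGlar plus retrieved IDegLira subjects; 50 imputations; ANCOVA on baseline; adjacent-visit correlation 0.85. Simplifications: no OAD or region factors, and intermediate visits of retrieved subjects treated as observed.

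| Retrieved at V32A | Approximation | Simulation (Monte Carlo error 0.003) | Mean Rubin SE |
|---|---|---|---|
| 100% | 0.735 | 0.735 | 0.098 |
| 50% | 0.718 | 0.719 | 0.102 |
| 0% | 0.701 | 0.703 | 0.105 |

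With none retrieved, correlations of 0.70 and 0.95 give 0.698 and 0.719. A simpler one-visit simulation gave 0.699, 0.719 and 0.727 at 0%, 50% and 100% retrieval.

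**6. More favourable assumptions, not in section 17.1.**

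- SD 1.0 is a raw SD and covariates explain 8% of variance (assumed). Residual SD = √0.92 = 0.959; power is 0.772 with complete data and 0.746 with none retrieved.
- True on-treatment benefit of 0.05% for IDegLira (assumed). The adjusted difference is 0.85 × (−0.05) + 0.15 × 0.3 = 0.0025; power is 0.857 with complete data and 0.846 with none retrieved.

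**The case against.** The shortfall is largely in the open. Section 17.1 calls the 80% nominal, ties it to PP, and in the next paragraph prints the penalised figure. Table 17–1 runs down to 0.479, and the 17-point span between SD 0.9 and 1.1 at 15% discontinuation (0.822 to 0.655) dwarfs the 3.4 points at issue. Leaving imputation variance out of a planning t-test is common practice.

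The lower end also depends on inputs the protocol does not give. If SD 1.0 is a raw SD, interpolating between 0.703 and 0.746 shows that about 6% explained variance (8% × 0.034/0.043) restores 0.737 even with no retrieval. Zero retrieval also runs against section 8.1.7, which brings discontinued subjects back for V32A at week 26.

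Much of this stands, and it limits the size of the point. The undisclosed part is small, and its lower end is a bound. It does not rescue the wording. Naming PP tells the reader which set was used, but the sentence still claims power for confirming an objective that PP cannot confirm. The penalised figure is introduced as an optional adjustment, whereas step 6 of section 17.3.1 makes the penalty mandatory. The minimum fails even within the table: the cell itself is 0.737, and power is 0.655 at SD 1.1 or 0.685 at 20% discontinuation. Section 17's own 15% missing-data figure sits badly with a calculation that assumes none.

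**Conclusion.** The concern holds. The arithmetic in section 17.1 is right, but the 80% describes a test that does not decide the primary objective, and the 74% is a complete-data figure rather than a minimum.

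Taking SD 1.0 as the residual SD (as Table 17–1 in effect does), true difference 0 and 15% discontinuation in each arm, the deciding analysis has about 70–74% power depending on V32A retrieval. The chance of failing the first test when the arms are truly equal is therefore about 26–30%, against the 20% a reader would infer. Of the gap to 80%, about 6 points (80 − 73.7) are already printed, and 0 to about 3.4 points (73.7 − 70.3) are not. Gains from covariates or a true IDegLira benefit would raise these figures, but section 17.1 assumes neither.

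**What to change.** Reword section 17.1 in three places:

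1. Describe the 80% as the power of an unpenalised t-test on the PP set, used for sizing, and drop the claim that it is the power for confirming the primary objective.
2. Replace the 74% minimum with about 74%, assuming complete week-26 data.
3. Add that power for the primary analysis (FAS, multiple imputation, non-inferiority penalty) is about 70–74% at SD 1.0 and 15% discontinuation, depending on V32A retrieval. State that SD 1.0 is taken as the residual SD and the true difference as 0.

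This costs wording only. N, the primary analysis and the test hierarchy are unchanged; the stated power becomes less favourable.

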17.2 Definition of analysis sets

The following analysis sets are defined in accordance with the ICH-E9 guidance $\frac{34}{2}$.

Full analysis set (FAS): includes all randomised subjects. In exceptional cases, subjects may be eliminated from the full analysis set. In such cases the elimination will be justified and documented. The statistical evaluation of the full analysis set will follow the ITT principle and subjects will contribute to the evaluation "as randomised".

Per-protocol (**PP**) analysis set: includes all subjects in the full analysis set who fulfils the following criteria:

- Have not violated any inclusion criteria
- Have not fulfilled any exclusion criteria
- Have a non-missing HbA_{1c} at screening or randomisation
- Have at least one non-missing HbA_{1c} after 12 weeks of exposure
- Have at least 12 weeks of exposure

Subjects will contribute to the evaluation "as treated".

Safety analysis set (SAS): includes all subjects receiving at least one dose of the investigational product or comparator. Subjects in the safety set will contribute to the evaluation "as treated".

Protocol		Date:	20 November 2015	Novo Nordisk
Trial ID: NN9068-4229	CONFIDENTIAL	Version:	2.0	
UTN: U1111-1168-9343	CONFIDENTIAL	Status:	Final	

Page:

73 of 107

Completer analysis set (CAS): includes all randomised subjects who have completed the trial without discontinuation from randomised treatment. Subjects in the completer analysis set will contribute to the evaluation "as randomised".

Randomised subjects who are lost to follow up and where no exposure information of the investigational product or comparators is available after randomisation will be handled as unexposed.

Before data are released for statistical analysis, a review of all data will take place to identify protocol deviations that could potentially affect the results. Any decision to exclude any subject or observation from the statistical analysis is the joint responsibility of the members of the study group. The subjects or observations to be excluded, and the reasons for their exclusion must be documented and signed by those responsible before database lock. The subjects and observations excluded from analysis sets, and the reason for this, will be described in the clinical trial report.

17.3 Primary endpoint

EudraCT No.: 2015-001596-48

17.3.1 Primary statistical analysis primary estimand

Multiple imputation – jump to reference – retrieved data – NI penalty

The primary objective of this trial is to confirm the effect of IDegLira in terms of glycaemic control in subjects with T2DM on previous treatment with SGLT2i ± OAD therapy.

The primary estimand for the primary objective will be the difference in change from baseline in HbA_{1c} after 26 weeks between T2DM subjects randomised to IDegLira and IGlar, both in combination with SGLT2i \pm OAD, regardless of whether subjects remained on initially assigned treatment or not until week 26. The treatment difference is to be compared to a non-inferiority margin of 0.3%.

Formally, let D be the mean treatment difference (IDegLira – IGlar) in change from baseline in HbA_{1c}. The null-hypothesis of IDegLira inferior by 0.3% or more will be tested against the alternative hypothesis of non-inferiority (IDegLira inferior by less than 0.3%) as given by

$$H_0$$
: $D \ge 0.3\%$ against H_A : $D < 0.3\%$.

Non-inferiority will be considered confirmed if the upper bound of the two-sided 95% confidence interval for D (mean treatment difference in change from baseline in HbA_{1c}) is strictly below 0.3%. This is equivalent to using a one-sided test of size 2.5%, i.e. the Type I error rate is controlled at 2.5% one-sided.

The primary estimand will be estimated based on the FAS using all post baseline HbA_{1c} measurements obtained at planned visits up to and including week 26, and data retrieved at week 26

CONFIDENTIAL

Date: Version: Status: Page:

20 November 2015 2.0 Final 74 of 107

Novo Nordisk

(V32A) from subjects prematurely discontinued from randomised treatment. To estimate this estimand for evaluation of non-inferiority of HbA_{1c}, a pattern mixture model approach³⁵ will be adopted. It mimics an ITT scenario where withdrawn and prematurely discontinued subjects from the investigational treatment (IDegLira) arm not having a week 26 measurement are assumed to be switched to a treatment inferior to comparator (IGlar) or any other treatment received after premature treatment discontinuation. This corresponds to a jump to reference (J2R) principle where a penalty in terms of the NI margin is added to withdrawn or prematurely discontinued subjects in the IDegLira arm. Observe that the J2R principle and use of retrieved (V32A) data in analyses will equalise treatment effects and in turn assay sensitivity in the non-inferiority setting may be jeopardized. The penalty of the non-inferiority margin³⁶ is to remedy this. Multiple copies (1000 copies) of the full dataset will be generated by imputing missing values based on estimated parameters for a subgroup of subjects in the trial. This will be done as follows:

- As a first step, all post-randomisation HbA_{1c} values for prematurely discontinued subjects in the investigational treatment group (IDegLira) not having retrieved (V32A) data are set to missing
- In the second step, intermittent missing values are imputed using a Markov Chain Monte Carlo (MCMC) method, in order to obtain a monotone missing data pattern. This imputation is done for each treatment group separately and 1000 copies of the dataset will be generated. Subjects from either group with retrieved (V32A) data will now have a non-missing data pattern
- In the third step, for each of the 1000 copies of the dataset, an ANOVA model with pre-trial OAD and region as factors, and baseline HbA_{1c} as covariate is fitted to the change in HbA_{1c} from baseline to first planned HbA_{1c} measurement visit after randomisation (V10) based on the control group (IGlar) and subjects with retrieved (V32A) data in the investigational group (IDegLira). The estimated parameters, and their variances, from this model are used to impute missing values at the first planned HbA_{1c} measurement visit after randomisation (V10) for subjects in both treatment groups, based on their pre-trial OAD, region and HbA_{1c} at baseline
- In the fourth step, for each of the 1000 copies of the dataset, missing HbA_{1c} values at the second planned HbA_{1c} measurement visit after randomisation (V14) are imputed in the same way as in the previous step, now based on an ANOVA model with pre-trial OAD and region as factors, and the HbA_{1c} values at baseline and at previous planned HbA_{1c} measurement visits as covariates, fitted to the control group (IGlar) and subjects with retrieved (V32A) data in the investigational group (IDegLira)
- This fourth step is then repeated sequentially over visits where HbA_{1c} measurement is planned, adding one visit in each step until the last planned visit (V32)
- In the sixth step a penalty equal to the non-inferiority margin 0.3% is added to the EOT HbA_{1c} value for any prematurely discontinued subject in the investigational group (IDegLira), irrespective of the EOT value being retrieved (V32A) data or an imputed value from the sequential imputation steps (step 3 to 5)

• In the seventh step, for each of the 1000 complete data sets, the change from baseline to the EOT visit (V32) is analysed using an ANOVA model with treatment, pre-trial OAD and region as factors and baseline HbA_{1c} value as a covariate

• In the eighth step, the estimates and standard errors for the 1000 data sets are pooled to one estimate and associated standard error using Rubin's rule³⁷. From these pooled estimates the confidence interval for the treatment difference and the associated *p*-value are calculated

